5.7.5.2 ITT Population

The ITT population will include all treated patients, who provide at least one post dose efficacy assessment. This will be the main population for all efficacy analyses.

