5.0 INVESTIGATIONAL PLAN

5.1 Overall Design and Plan of the Study

This is an open label phase IIa pilot study to be conducted in six (6) patients with acute AIS during a 6-weeks period [REDACTED]

To determine eligibility for entry into the study, [REDACTED]
[REDACTED] Eligible patients will be enrolled and will be administered [REDACTED]
[REDACTED]

[REDACTED]

[REDACTED]

The results will be reviewed on the basis of a benefit: risk assessment. If the benefit: risk assessment is in favour of afamelanotide, in the opinion of the Investigator, [REDACTED]

Radiological evaluation by assessing the imaging from Computed Tomography Perfusion (CTP)

Clinical evaluations will be performed by accredited study staff over the course of the study. The NIHSS will be performed at the Day of Admission (Day 0) and on Days 1, 2, 3, 4, 7, 8 and 42 or Premature Termination Visit (if applicable). The modified Rankin Scale (mRS) will be performed on Days 0, 7 and 42 or Premature Termination Visit (if applicable). [REDACTED]

Safety assessments (review of AEs and concomitant medications) will be carried out each day (each study visit from the Day of Admission to Day 8 and Day 42 or Premature Termination Visit).

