5.2.1 Inclusion Criteria

The patients have to fulfill all of the following *inclusion criteria* for study participation:

5.2.4 *Withdrawals and Replacement of Patients*

A discontinuation occurs when a patient does not complete the study as required by the study protocol. Patients will be free to discontinue their participation in this trial at any time for any reason. In addition, patients may be withdrawn from the trial at the discretion of the Investigator or medically qualified nominee. A patient may be withdrawn for any of, but not limited to, the following reasons:

- Informed consent withdrawn by the patient or medical treatment decision maker;
- AE requiring study discontinuation;
- When the Investigator's or nominee's best professional judgment would indicate that it would be in the patient's best interest to be withdrawn;
- Violation of inclusion/exclusion requirements.

The reasons for withdrawal or discontinuation of a patient will be recorded in the patient's medical notes and CRF. If an AE is the reason for discontinuation, the event must be followed up and documented as described in the 5.5.3.2 Safety variables of the protocol. If the patient discontinued for any reason after the enrolment into the study, a study Premature Termination visit, as described in 5.5.1, should be performed at the time of study discontinuation, or as soon as possible after discontinuation. This visit will be documented in the patient's medical notes and CRF.

Any patient(s) withdrawn from the trial prior to their completion for any reason will not be replaced. Data compiled to the point of discontinuation will be used for 'intent to treat' (ITT) analysis. Patients violating any of the inclusion and exclusion criteria will be described as protocol deviators.

5.3 **Study Medication**

5.3.1 *Description of Study Medication*

[REDACTED] afamelanotide
[REDACTED]
[REDACTED]

5.3.2 *Treatment Groups*

There is one treatment group in this study (Open-label study). As such, all patients who satisfy the inclusion/exclusion criteria will be allocated a study subject number and receive afamelanotide. Study subject number allocation will be detailed in the CUV801 Study Operating Manual (SOM).

The groups consist of:

- **Six (6) stroke patients with acute distal (M2 and beyond) LVO or perforator occlusion.**

Open label study: Six (6) patients receiving afamelanotide.

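### The main efficacy population is called ITT but is a modified ITT set: a treated patient with no post-dose efficacy assessment is left out of the secondary efficacy results, and section 5.2.4 carries no such condition

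*Combined protocol and SAP*

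**What the plan says.** Section 5.7.5.2 defines the population: "The ITT population will include all treated patients, who provide at least one post dose efficacy assessment". It adds: "This will be the main population for all efficacy analyses".

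Section 5.2.4 (Withdrawals and Replacement of Patients) covers discontinued patients. On replacement: "Any patient(s) withdrawn from the trial prior to their completion for any reason will not be replaced". On the use of their data: "Data compiled to the point of discontinuation will be used for 'intent to treat' (ITT) analysis". It does not require a post-dose assessment. The same section asks for a Premature Termination visit for anyone who discontinues after enrolment, which "should be performed at the time of study discontinuation, or as soon as possible after discontinuation".

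Section 5.1 places both clinical scales at that visit. After Day 0 the NIHSS is done "on Days 1, 2, 3, 4, 7, 8 and 42 or Premature Termination Visit (if applicable"), and the mRS "will be performed on Days 0, 7 and 42 or Premature Termination Visit (if applicable").

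Section 5.7.5.1 puts every enrolled patient in the Safety Population, which serves the primary endpoint. Section 5.7.4 plans six patients, a number set by availability. The text of 5.7.5.3 (missing data) and 5.7.5.4 (per protocol) is blacked out in the public copy.

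**The concern.** A set that requires a post-dose assessment is selected on a post-treatment event. In acute stroke, a patient with no such assessment is unlikely to be missing for reasons unrelated to outcome; death before the first score is the plainest case. Reporting the remaining patients as ITT suggests that all treated patients are counted when they may not be, and the omission tends to make the efficacy summary look better.

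The plan also gives two rules for one patient. If the only efficacy data are from baseline, 5.2.4 uses them in the ITT analysis and 5.7.5.2 removes the patient from the ITT set. With six patients, that choice should not be left until the results are known.

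**Working it through.** There is no power calculation or other derived figure to reproduce, since the sample size rests on availability. The check compares the sections and then sizes the effect of one exclusion.

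**1. The sections side by side, for treated patients.** Section 5.2.4 treats any failure to complete the study as a discontinuation, so a death falls under it.

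| Treated patient | ITT set (5.7.5.2) | 5.2.4 | Safety Population (5.7.5.1) |
|---|---|---|---|
| Discontinues after at least one post-dose score | in | data used | in |
| Withdraws before any scheduled score, attends the Premature Termination visit | in, because NIHSS and mRS are done there | data used | in |
| Withdraws before any scheduled score, misses or refuses that visit | out | baseline data used | in |
| Dies before any post-dose score | out | baseline data used | in |

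The sections agree in the first two rows and differ in the last two.

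**2. Size of one exclusion.** Planned number 6 (5.7.4), no replacement (5.2.4): 1/6 = 16.7% of the sample.

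**3. Effect on a proportion (assumed illustration).** The visible plan has no responder endpoint, so 'improved' is only a device here. Suppose one treated patient dies before any post-dose score.
- Other five all improve: 5/5 = 100% (exact 95% CI 47.8% to 100%) as defined now; 5/6 = 83.3% (35.9% to 99.6%) with all treated patients.
- Three of the other five improve: 3/5 = 60% as defined now; 3/6 = 50% with all treated patients.
- Poor outcomes in the first case: 0/5 as defined now; 1/6 = 16.7% (0.4% to 64.1%) with all treated patients.

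**4. Effect on a test.** The synopsis sets a two-sided level of 0.05 and section 5.7 names non-parametric analyses without a visible specific test. Assume an exact signed-rank or sign test. The smallest attainable two-sided p is 2/2^n.
- n = 6: 2/64 = 0.03125.
- n = 5: 2/32 = 0.0625.

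With five improving and the death ranked worst among six, the signed-rank p is 2 × 14/64 = 0.4375 and the sign-test p is 2 × 7/64 = 0.219. The p-value moves from 0.0625 to one of these. It is above 0.05 under either population.

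**5. How often.** The documents give no rate. If each patient has probability q of having no post-dose assessment, the chance of losing at least one of six is 1 − (1 − q)^6.

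| Assumed q | Chance of at least one exclusion |
|---|---|
| 2% | 11% |
| 5% | 26% |
| 10% | 47% |
| 20% | 74% |

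Given the early NIHSS schedule and the Premature Termination visit, the lower rows of q seem more plausible, but that is a judgement.

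**The case against.** The strongest defence has five parts.

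- **Withdrawal is mostly covered.** A reader might infer that anyone withdrawn soon after dosing is lost. The documents do not support that. The Premature Termination visit includes NIHSS and mRS, and for a dosed patient it is a post-dose efficacy assessment. Only a patient who misses or refuses it is excluded. This stands and limits the point. The visit cannot help after a death.
- **Early deaths are not hidden.** A reader might infer that an early death disappears from the trial's results. It does not. The patient is in the Safety Population, death from any cause is a serious adverse event (5.5.3.2.5), and serious events are listed individually (5.7.5.8). Only the secondary, exploratory efficacy results are affected. This stands.
- **Section 5.2.4 is about data use.** It does not define a population, and a patient with baseline data alone has no change from baseline to contribute. So a general contradiction between the sections is too strong a reading. The narrow difference remains, because a death can be counted as an outcome without a measured change.
- **Blacked-out text may answer part of it.** Section 5.7.5.3 may hold a rule for deaths, so its absence cannot be asserted. Visit procedures and dosing times are also blacked out. Day 1 is the first NIHSS visible after Day 0, but a post-dose score on Day 0 cannot be excluded. Appendix A is blacked out too, so the mRS grade for death cannot be taken from the documents.
- **Exclusion does not create significance.** Under the assumed tests, five patients cannot reach 0.05. The distortion is in the descriptive results.

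None of this makes the ITT label accurate, and the visible wording still decides who enters the set.

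**Conclusion.** The point holds in a limited form. The main efficacy set is a modified ITT set under an ITT label. On the visible text it omits treated patients who die before any post-dose efficacy assessment, or who withdraw and do not have the Premature Termination visit. For those patients, whose efficacy data are baseline only, 5.2.4 and 5.7.5.2 give different answers.

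The effect is confined to secondary efficacy results and should arise rarely. When it does, it removes 16.7% of a sample that is not replenished and shifts a summary in the favourable direction (5/5 instead of 5/6 in the assumed example). This rests on the visible text, on an assumed responder measure and on assumed exclusion rates. A rule in the blacked-out missing-data section could reduce the point further. It is worth correcting because the change is small and can be made before any result is seen.

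**What to change.** - In 5.7.5.2, define the main efficacy population as all patients who received any afamelanotide, and align 5.2.4 with it.
- Use all treated patients as the denominator for the Day 7 and Day 42 summaries.
- Count a death before assessment as the worst outcome category on the scale concerned, and check that 5.7.5.3 agrees.
- List every treated patient with no post-dose value, with the reason.
- If the present set is kept, call it modified ITT and use it as supportive only.

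The cost is wording in two sections, plus consistency with the missing-data section. No new data or visits are needed. The efficacy summaries may come out slightly less favourable.

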5.7.5.3 Handling of Missing and Incomplete Data

[REDACTED]

[REDACTED]

[REDACTED]

[REDACTED]

5.7.5.4 Per Protocol Analysis (PPA) Population

[REDACTED]

5.7.5.5 Demographic and Initial Characteristics

Demographic and baseline characteristics will be summarized using descriptive statistics.

5.7.5.6 Efficacy

Primary and secondary efficacy endpoints are described under section 5.5.3.1 Efficacy variables of the Study Protocol.

[REDACTED]

5.7.5.7 Safety

Descriptive methods will be used to summarize the safety data. These will be based upon the safety population.

5.7.5.8 Adverse Events

All AEs, including non-TEAEs, will be listed. A TEAE is defined as:

- An event that was not present prior to or on the day of the first study medication administration but was present after study medication was administered.
- An event that was present prior to first administration of study medication and continued to occur after the administration of the first dose at an increased level of severity.

[REDACTED]

- An event that was present prior to administration of study medication and was documented as completely resolved and re-emerged after the administration of the first dose.

The MedDRA AE dictionary will be used to map verbatim AE terms to preferred terms and body systems. The number of patients with TEAEs will be summarized by preferred term and body system. TEAEs will be further summarized by intensity, seriousness and relationship to study medication. The number of patients who terminate treatment early due to AEs related to study medication will be tabulated. Summaries of the incidence of toxicities will be prepared, as appropriate.

SAEs, SUSARs, and AEs of special interest will be listed individually. Any SAE that occurs prior to the first dose of the study medication, will be documented in the study report.

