To be eligible to enter the study, patients must meet the following *inclusion criteria*:

- Male or female subjects with a diagnosis of first AIS due to distal [M2 segment and beyond] occlusion or perforator occlusion
- [REDACTED]
- Mild to moderate stroke severity [REDACTED]
- [REDACTED]
- Aged 18- 85 years
- Written informed consent obtained from patient and/or medical treatment decision maker prior to study-start (upon admission).

To be eligible to enter the study, patients must not meet any of the following *exclusion criteria*:

- Administration of intravenous thrombolytic therapy in distal occlusion as etiology of AIS
- Intervention by endovascular thrombectomy (EVT)
- [REDACTED]
- Any evidence of hepatic (defined as three times standard range) or [REDACTED]
- [REDACTED]
- [REDACTED]
- [REDACTED]
- [REDACTED]
- [REDACTED]
- [REDACTED]
- [REDACTED]

Test product:

Afamelanotide [REDACTED]

Dose: [REDACTED]

Mode of administration: Subcutaneous administration

Reference therapy:

None

Study Endpoints:**Primary Endpoints**

(i) Evaluate the safety of afamelanotide by monitoring and recording treatment-emergent adverse events (TEAEs) (on all days of administration and up to day 42).

Secondary Endpoints

- (i) Evaluate changes in reperfusion of the ischaemic core and the penumbral ischaemic zone (salvageable tissue)
- (ii) Evaluate neurological functions, cognitive functions, daily activities

Statistical Methods (exploratory):**Primary Endpoints****Safety Analyses:**

The number of participants with TEAEs will be summarized by Medical Dictionary for Regulatory Activities (MedDRA) preferred term and body system. TEAEs will be further summarized by intensity, seriousness, outcome and relationship to study drug. Participants who prematurely terminate treatment due to AEs related to study medication will be summarized.

Secondary Endpoints

An evaluation will be made of *changes in the reperfusion of the ischaemic core and the penumbral ischaemic zone* (salvageable tissue) [REDACTED]

In this exploratory analysis, the null hypothesis is formulated as:

H₀: there is no change to the ischaemic core and or penumbral ischaemic zone following the administration of afamelanotide 16mg.

Following changes observed from cerebral imaging, standard clinical outcomes will be monitored.

An evaluation will be made of

- (1) changes of neurological function as measured by NIHSS on Days 1, 2, 7 and 42 compared to baseline

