5.3.3 Dosage and Administration of Study Medication

Afamelanotide [REDACTED] will be administered [REDACTED] on the designated study days. [REDACTED]

[REDACTED]. Please refer to the CUV801 SOM for further details.

[REDACTED]
[REDACTED]
always within 24 hours of onset of symptoms or last seen well.

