5.3.6 Compliance

Data related to the administration of the study drug will be recorded on the CRF.

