5.5.3.2.5 Adverse Events

An adverse event (AE) is defined as any untoward medical event (clinical or laboratory) experienced by a patient during the course of a clinical trial, whether or not it is related to the investigational product. An AE may be a symptom, sign, or abnormal finding or test result. Whenever possible, the Investigator will group together into a single term, signs and symptoms that constitute a single diagnosis. For example, cough, rhinitis and sneezing might be grouped together as "upper respiratory tract infection".

The Investigator will monitor each patient closely for the development of AEs, and any adverse experience spontaneously reported by or elicited from the patient or observed by the Investigators (physician or study staff) will be recorded in the patient's medical notes and on the appropriate AE page of the CRF, when applicable. [REDACTED]

[REDACTED]
[REDACTED]
[REDACTED]

[REDACTED] It is the responsibility of any member of the study site staff to immediately report any suspected AE to the Investigator.

The Investigator will assess the AE(s) in the patient's medical notes and provide the date and time of onset, severity, seriousness, action taken, outcome, date of resolution (or comment that the event is still continuing) and relationship to study medication.

If a laboratory value is outside the normal range, the Investigator must comment on the findings in the laboratory report. For any clinical laboratory abnormality, the Investigator will make a judgment as to clinical significance. All clinically significant laboratory abnormalities will be recorded as an AE in the patient's medical notes and on the AE page of the CRF.

All AEs will be followed up in accordance with GCP. AEs will be graded for severity as defined below:

- **Mild** - The AE is transient and easily tolerated by the patient. Specific action is optional;
- **Moderate** - The AE causes the patient discomfort and interrupts the patient's usual activities;
- **Severe** - The AE causes considerable interference with the patient's usual activities and may be incapacitating or life-threatening.

Outcome of the event must be described as one of the following:

- Recovered without sequelae;
- Recovered with sequelae;
- Recovering;
- Not recovered;
- Death.

The Investigator will be asked to document his/her opinion of the relationship of the event to the study drug as follows:

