5.7.2 Efficacy Assessment

5.7.2.1 Specification of Efficacy Endpoints

Primary Endpoints

- (i) *Evaluate the safety of afamelanotide* by monitoring and recording TEAEs (on all days of administration and up to day 42).
TEAEs will be recorded and coded as MedDRA Preferred Terms.

Secondary Endpoints

- (i) *Evaluate changes in the reperfusion of the ischaemic core and the penumbral ischaemic zone* (salvageable tissue) by quantitative analysis of hemodynamics:

[REDACTED]

- [REDACTED]
- [REDACTED]
- [REDACTED]

Upon completion of the study, each patient will generate efficacy after comparing the DWI-FLAIR on Days 3(\pm 1) and 9(\pm 1) with the CTP on Day 0 (Day of Admission).

[REDACTED]

[REDACTED]

[REDACTED]

[REDACTED]

[REDACTED]

5.7.3 *Safety Assessment*

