5.7.3.1 Specification of Safety Endpoint (Primary Endpoint)

The safety endpoint will be the incidence of TEAEs occurring during the study period, including clinically significant changes in laboratory parameters, will be listed by intensity, seriousness, outcome, and relationship to study drug.

5.7.4 *Sample Size*

While this is a phase IIa study of common indication, the sample size is based on availability of patients. A total of six (6) patients are planned to be enrolled in this study. This constitutes an open-label exploratory study.

5.7.5 *Analysis Plan*

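### As legibly written, the TEAE definition drops new adverse events that start after the first dose on the same calendar day, although the primary endpoint is meant to count them

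*Combined protocol and SAP*

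**What the plan says.** The primary endpoint is safety, assessed by "monitoring and recording TEAEs (on all days of administration and up to day 42" (section 5.7.2.1); the synopsis says the same. Section 5.7.3.1 makes it a rate: "The safety endpoint will be the incidence of TEAEs occurring during the study period".

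Section 5.7.5.8 decides which events are TEAEs. Three criteria are legible, and meeting any one is enough:

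1. New event: "An event that was not present prior to or on the day of the first study medication administration", but present after study medication was given.
2. Worsening: present before the first administration and continuing afterwards at greater severity.
3. Re-emergence: present before administration, documented as fully resolved, then back after the first dose.

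A redacted block stands between the second and third criteria.

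The same section lists all AEs whether or not they are TEAEs, and adds that "SAEs, SUSARs, and AEs of special interest will be listed individually". The counts by preferred term and body system, and the breakdowns by intensity, seriousness and relationship, are of TEAEs.

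**The concern.** The first criterion is the only legible route for an event that did not exist before treatment, and it is tied to the calendar day of the first dose, not to the dose itself. Everything new on that day is excluded, including what follows the dose. The other two criteria, and the sentence in section 5.7.5.8 on SAEs before the first dose, are all tied to the administration. A new SAE some hours after dosing is thus neither a pre-dose SAE nor a TEAE.

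The day matters. Section 5.3.3 places dosing "always within 24 hours of onset of symptoms or last seen well", so the first dosing day lies in the acute phase of the stroke. It is also the first day on which an administration reaction, new bleeding or another new-onset event could follow the drug. Such events would be missing from TEAE incidence and from every TEAE breakdown. The omission can only make the drug look safer, and there is no control arm in which the same omission would occur.

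**Working it through.** **Step 1: apply the definition.** The three legible criteria are joined by *or* and applied to five kinds of event. The last column replaces criterion 1 with onset at or after the time of the first dose.

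| Event | Crit. 1 | Crit. 2 | Crit. 3 | TEAE as written | TEAE if tied to dose time |
|---|---|---|---|---|---|
| New, after the dose, same day | no | no | no | **no** | **yes** |
| New, later day | yes | no | no | yes | yes |
| Present before dose, worsened | no | yes | no | yes | yes |
| Present before dose, resolved, re-emerged | no | no | yes | yes | yes |
| Present before dose, unchanged | no | no | no | no | no |

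Only the first row changes. A same-day new event that persists or worsens on later days stays in that row: it was present on the dosing day and absent before the dose.

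**Step 2: compare with the endpoint.** The first dosing day is a day of administration, so sections 5.7.2.1 and 5.7.3.1 include it. Section 5.7.5.8 removes its new events. The sections conflict.

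**Step 3: size in this trial.** The plan gives no target rate or power figure to reproduce; section 5.7.4 sets n = 6 by patient availability. One patient is 1/6 = 16.7 percentage points. Exact (Clopper-Pearson) 95% intervals:

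- 0/6 = 0%: 0 to 45.9% (upper limit 1 − 0.025^(1/6) = 0.459)
- 1/6 = 16.7%: 0.4% to 64.1%

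**Step 4: how likely an effect is.** The documents give neither quantity below, so both are assumptions shown over a range:

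- p = chance that a patient has a new post-dose event on the first dosing day
- q = share of those patients who also have another, countable TEAE by Day 42

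Chance that at least one patient has an event dropped from the TEAE tables: 1 − (1 − p)^6. For p = 0.1 this is 1 − 0.9^6 = 0.469.

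Chance that overall TEAE incidence changes: 1 − (1 − p(1 − q))^6. For p = 0.1 and q = 0.5 this is 1 − 0.95^6 = 0.265.

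Expected number of patients losing TEAE status: 6p(1 − q).

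| | p = 10% | p = 20% | p = 30% |
|---|---|---|---|
| At least one patient with a dropped event | 46.9% | 73.8% | 88.2% |
| Incidence changes, q = 50% | 26.5% | 46.9% | 62.3% |
| Incidence changes, q = 80% | 11.4% | 21.7% | 31.0% |
| Expected patients lost, q = 0 | 0.6 | 1.2 | 1.8 |
| Expected patients lost, q = 50% | 0.3 | 0.6 | 0.9 |
| Expected patients lost, q = 80% | 0.12 | 0.24 | 0.36 |

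The first row is an upper bound on the chance that overall incidence changes (the case q = 0).

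**The case against.** The strongest objection is the redaction. To say that no criterion catches these events is a claim about a whole list, and part of the list is hidden. The block may hold a further criterion or nothing of substance. This stands as a limit on certainty. It does not make criterion 1 sound: if a hidden criterion covers these events, the two need aligning.

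Second, the events do not disappear. All AEs are listed. SAEs, SUSARs and AEs of special interest are listed individually. Early terminations due to related AEs are tabulated, and toxicity summaries are planned as appropriate, with no TEAE condition stated for either. Any SAE goes to the sponsor within 24 hours of awareness, and AEs are reviewed at each visit. With six open-label patients a reader could check every event. All of this is true, and patient monitoring does not depend on the definition. But the endpoint is the incidence of TEAEs, and none of these measures returns the event to that figure.

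Third, no legible test, threshold or stopping rule uses TEAE incidence, the safety analysis is descriptive, and the two intervals overlap heavily. That is fair, and it limits the consequence to a misreported primary result. Worsening of the presenting deficit on the first day is also not lost, since criterion 2 covers it.

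Fourth, an analyst reading the sections together would probably include first-day events. Perhaps so, but the wording contains no pre-dose qualifier, and a programmer following it literally would exclude them.

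**Conclusion.** The concern holds on the legible text. Criterion 1 of the TEAE definition contradicts the stated scope of the sole primary endpoint and gives a wrong classification for new post-dose events on the first dosing day. The direction is certain: TEAE counts can only fall. Each patient whose only event is of this kind costs 16.7 points of incidence. How often that would happen cannot be known from the documents. Over the assumed ranges, the chance that overall incidence changes runs from 11.4% (p = 10%, q = 80%) to 88.2% (p = 30%, q = 0). Even where it does not change, the preferred-term, intensity, seriousness and relationship tables can be incomplete. The conclusion rests on the redacted block not already covering these events. It should be corrected before analysis, because it affects the only primary endpoint and the remedy is small.

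**What to change.** Reword the first criterion in section 5.7.5.8 as: *an event with onset at or after the date and time of the first study medication administration*. Add that an event on that day is counted as treatment-emergent if its onset time or the dose time is unknown. Keep the worsening and re-emergence criteria. If the redacted block already deals with new post-dose events on the first day, align the first criterion with it.

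The core change is one sentence. Section 5.5.3.2.5 already has the investigator "provide the date and time of onset, severity, seriousness, action taken, outcome", so onset can be placed before or after the dose. On dosing, section 5.3.6 says "Data related to the administration of the study drug will be recorded on the CRF". The legible text does not say that the clock time of the dose is captured, and the unknown-time rule covers that gap. The price is that the reported TEAE count may rise, because some first-day stroke complications will be counted, including a few of unknown timing that may have preceded the dose. For a safety endpoint that is the conservative direction.

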4.0 STUDY OBJECTIVES

4.1 Primary Objective

The objective of this pilot study is to evaluate the safety of afamelanotide in AIS patients.

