5.5.3.2 Safety Variables

The number of patients with treatment-emergent AEs (TEAEs) will be summarized by MedDRA preferred term and body system. TEAEs will be further summarized by intensity, seriousness, outcome and relationship to study drug. Patients who prematurely terminate treatment due to AEs related to study medication will be summarized.

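### In the visible text, early termination of treatment is counted only for AEs judged related to the drug; a count for any AE, split by relationship, would complete the safety table

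*Combined protocol and SAP*

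**What the plan says.** Three places in the combined protocol and SAP plan a summary of early treatment termination, and all three carry the same restriction.

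- Section 5.7.5.8 (Adverse Events): "The number of patients who terminate treatment early due to AEs related to study medication will be tabulated".
- Section 5.5.3.2 (Safety Variables): "Patients who prematurely terminate treatment due to AEs related to study medication will be summarized".
- Protocol Synopsis, Safety Analyses: "Participants who prematurely terminate treatment due to AEs related to study medication will be summarized".

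The setting is given elsewhere. Section 4.1 reads "The objective of this pilot study is to evaluate the safety of afamelanotide in AIS patients", and Section 5.1 reads "This is an open label phase IIa pilot study to be conducted in six (6) patients with acute AIS". On causality, Section 5.5.3.2.5 says "The Investigator will be asked to document his/her opinion of the relationship of the event to the study drug" and offers three categories: Related, Not Related and Not Assessable.

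The other AE outputs have a wider scope. Section 5.7.3.1 defines the safety endpoint as TEAE incidence with no causality condition. Section 5.7.5.8 lists all AEs, lists SAEs individually, and summarises TEAEs by intensity, seriousness and relationship; the Synopsis and Section 5.5.3.2 add outcome.

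**The concern.** Stopping treatment because of an AE is a basic tolerability result, and safety is this trial's primary objective. For TEAEs the plan counts every event and then splits by relationship. For early termination it filters by relationship first and counts what is left. In the visible text this is the only AE count treated that way.

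The filter is one person's unblinded judgement, with no control arm to set it against. Acute stroke supplies a ready alternative explanation for many events, and an alternative explanation is one of the stated grounds for Not Related. Not Assessable matters more. It is defined for reports that point towards a reaction but cannot be judged because the information is too thin or conflicting. A patient who stops treatment for a suspected but unverifiable reaction would, on a literal reading, be left out of the termination count.

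What is at stake is the completeness of one descriptive safety row, not the validity of the primary endpoint.

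**Working it through.** **1. Can treatment end early?** The dosing schedule is redacted. The Synopsis has TEAEs monitored "on all days of administration and up to day 42", and Section 5.3.3 has the drug given "on the designated study days". Both are plural, which indicates more than one administration day. The pregnancy and breastfeeding text in Section 5.5.3.2.5 also refers to a treatment period and foresees patients being taken off treatment. Early termination is therefore a possible event.

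**2. Who falls outside the planned row?** Setting the three relationship categories against the three termination statements gives:

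| AE that led to stopping | In the planned termination row? | In the TEAE summary by relationship? | In the AE listing? |
|---|---|---|---|
| Related | Yes | Yes, if a TEAE | Yes |
| Not Related | No | Yes, if a TEAE | Yes |
| Not Assessable | No, read literally | Yes, if a TEAE | Yes |

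The last two columns show that the event is reported. They do not show that it led to stopping: no visible TEAE breakdown is by action taken or discontinuation, and the visible text does not say that the listing shows action taken.

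**3. Size.** The only input is n = 6 (Section 5.7.4), which was set by patient availability, so there is no sample-size figure to reproduce. For x patients out of n, the exact (Clopper-Pearson) two-sided 95% limits are the 2.5% quantile of Beta(x, n − x + 1) and the 97.5% quantile of Beta(x + 1, n − x), with a lower limit of 0 when x = 0.

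- x = 0: 0/6 = 0%; upper limit 1 − 0.025^(1/6) = 45.9%; interval 0 to 45.9%.
- x = 1: 1/6 = 16.7%; lower limit 1 − 0.975^(1/6) = 0.4%; interval 0.4 to 64.1%.
- x = 2: 2/6 = 33.3%; interval 4.3 to 77.7%.

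Suppose one patient stops for an AE rated Not Related or Not Assessable and nobody stops for a Related one. The Related row shows 0/6, and an any-AE row would show 1/6. With two such patients the rows would show 0/6 and 2/6. Each patient is worth 1/6 = 16.7 percentage points. The documents give no expected rate of AE-driven stopping, so no probability of this happening is claimed. The visible text does not plan these intervals; they are shown for scale only.

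**4. Is stopping treatment distinct from leaving the study?** Section 5.2.4 defines discontinuation as not completing the study, allows withdrawal for an AE with no causal condition, and has the reason recorded in the notes and CRF. The pregnancy text in Section 5.5.3.2.5 has patients withdrawn from treatment complete the Premature Termination Visit, which Section 5.2.4 ties to study discontinuation. The visible text does not cleanly separate the two events.

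**The case against.** The strongest reply is that this is a reporting preference. The three statements agree with one another, and nothing in the plan is contradicted. All AEs are listed, SAEs are listed individually, and withdrawal reasons and drug administration go on the CRF (Sections 5.2.4 and 5.3.6). With six patients, a reader could go through the cases one by one. The definition of Related is also fairly inclusive, since a reasonable possibility of a causal link is enough. A wider count could not be attributed to the drug without a control arm.

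Most of this stands, and it is why the point is minor. It does not close the gap. No visible summary counts AE-driven stops regardless of cause. The listing would serve as a substitute only if it shows action taken, which the visible text does not state. An inclusive definition of Related does not bring Not Assessable events into the row.

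A second reply is that heavy redaction makes absence from the visible text weak evidence. That is fair. Parts of Sections 5.5, 5.7, 5.7.5.8 and 5.7.5.11, and the bodies of 5.7.5.3, 5.7.5.4, 5.7.5.9 and 5.7.5.10, are blacked out, and any of them could hold a disposition or any-AE count.

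A reader might also infer that the planned table would be wrong, reporting 0/6 where the true figure is 1/6. The documents do not support that. The row is labelled as related, and 0/6 would be the correct value for that label.

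**Conclusion.** The point holds as a minor gap in reporting. The three visible statements set a consistent rule that counts early termination only for related AEs, and this departs from the plan's own approach to TEAEs. In an uncontrolled, open-label safety trial that leaves the tolerability summary incomplete, most clearly for Not Assessable events. For one affected patient, the difference is between a related row of 0/6 and an any-AE row of 1/6.

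It would go too far to infer that the primary safety result is biased or that AEs are suppressed. TEAE incidence carries no causality filter, the listings cover all AEs, and the visible text attaches no test, threshold or decision to this count. Nor do Sections 5.2.4 and 5.7.5.8 contradict each other: one governs withdrawal and recording of the reason, the other a tabulation.

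The conclusion rests on three assumptions: the related-only wording is applied literally, treatment is given on more than one day, and no redacted section already holds the wider count.

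**What to change.** In the Synopsis, Section 5.5.3.2 and Section 5.7.5.8, replace the related-only statement with a tabulation of patients who terminate treatment early because of any AE, with rows for Related, Not Related and Not Assessable. Add a separate row for withdrawal from the study due to an AE only if the CRF distinguishes it from stopping treatment. If redacted text already provides an any-AE count, cross-refer to it in the three places instead.

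The cost is wording in three places and one small table. Sample size, alpha and the primary endpoint do not change. One check is needed first: Section 5.5.3.2.5 has the action taken for each AE assessed in the medical notes, so confirm that the CRF captures the reason for stopping treatment. The downside is a possibly higher reported count that cannot be attributed to the drug without a control arm; the split by relationship lets the reader see that.
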